5.4 Breaking the Blind

The Investigator will be allowed to break the blind if, in his/her opinion, this is necessary to provide proper medical care to his/her patient. In general, study drug unblinding should not impact any necessary treatment decisions by the investigator. Prior to breaking the blind, the Investigator will confer with the Medical Monitor to confirm the necessity of such action.

In the absence of the Investigator, the Medical Monitor may break the blind for a specific study subject under such urgent circumstances and after assessing the necessity of such action with a sub-investigator.

Members of the Data Monitoring Committee (DMC) will be allowed to break the blind if it is deemed necessary to assess specific adverse events.

The circumstances leading to breaking the blind will be fully documented in detail in a memo to file and as required, in the EDC system.

5.5 Drug Supplies

Aerucin[®] is a fully human IgG1 lambda monoclonal antibody that binds to alginate on the surface of all *P. aeruginosa* cells and mediates complement-dependent phagocytic killing of both mucoid and non-mucoid *P. aeruginosa*.

5.5.1 Formulation and Packaging

The Aerucin[®] drug product is formulated at 27.5 mg/mL in 10 mM L-histidine, 150 mM sodium chloride, pH 6.0, and 0.02% w/v Polysorbate 20. Aerucin[®] is a clear to slightly opalescent, colorless to pale yellow, sterile, preservative-free liquid for intravenous infusion. The composition of the Aerucin[®] drug product is provided in the table below.

The composition and formulation of the placebo is the same but for the absence of Aerucin[®].

Table 5-1 Composition of Aerucin[®] Drug Product

Ingredient	Amount/mL	Function
Aerucin [®]	27.5 mg/mL	Active ingredient
L-Histidine	0.80 mg/mL	Buffer
L-Histidine (monohydrochloride, monohydrate)	1.01 mg/mL	Buffer
Sodium chloride	8.77 mg/mL	Tonicity, Stabilizer
Polysorbate 20	0.2 mg/mL	Stabilizer
Water for Injection, USP	q.s.	Solvent

Abbreviations: mg/mL = milligram(s) per milliliter; q.s. = quantum satis

The study drug (investigational product or control) is provided in 10 mL glass vials with butyl rubber stoppers containing no less than 4.5 mL of extractable volume at an Aerucin[®] concentration of 27.5 mg/mL. Each vial is labeled in the local language in compliance with local regulations. Each vial is identified with a unique vial number.

The vials are packaged in individual cartons (one per vial), similarly labeled.

5.5.2 Study Drug Preparation and Dispensing

Upon randomization, the number of vials of study drug based on subject's weight required for treatment will be displayed by the EDC / IWRS system, and access will be given to the inventory corresponding to the treatment allocation of the subject.

Study personnel will then select the specific vials required, up to a maximum of 20 vials from the inventory available on site. Subjects weighing over 120 kg will receive the amount of Aerucin[®] or placebo corresponding to 120 kg, i.e. 20 vials.

A Pharmacy Manual will describe the process in detail. In summary, to prepare the study drug for use, the corresponding volume of liquid from the study drug must first be extracted from a 100 mL normal saline infusion bag, and then the content of the selected vials must be transferred into this bag using sterile technique.

When ready for use, the infusion bag should be marked with the study subject number, the date and time of preparation, and the number of vials used, and a list of the vial numbers that were used for verification against the list assigned using the EDC / IWRS system should be provided.

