1.2 Aerucin[®]

Aerucin[®] binds to the conserved epitope of *P. aeruginosa*, alginate, at the C6 carboxyl group of mannuronic acid and mediates complement dependent phagocytic killing of both mucoid and non-mucoid *P. aeruginosa*. Our data show that alginate is present on >90% of clinical *P. aeruginosa* isolates tested, and that there is no non-specific binding of Aerucin[®] against a panel of 40 normal human tissues. Opsonization is a key feature of Aerucin's mechanism of action as demonstrated in vitro: phagocytic assays showed that enabling *P. aeruginosa* killing requires the presence of phagocytes (e.g., neutrophils, macrophages) and complement. Its binding target (alginate) is a common cell surface component of *P. aeruginosa* and is critically required for host colonization and pathogenicity. Indeed, if selection pressure resulted in down regulated expression of alginate (which is not known to occur naturally), *P. aeruginosa* would become unable to colonize the host and significantly more susceptible to conventional antibiotics. Aerucin[®] offers additional features that may be advantageous compared to conventional small molecule antibiotics for use in pneumonia and in CF, including long systemic serum half-life of about 3 weeks, and thus requires much less frequent dosing than antibiotics. As a result, Aerucin[®] offers a unique profile and an entirely new mode of action, with no direct competition from antibiotics.

Aerucin[®] has not yet been approved for human use. Cellular and animal studies conducted with Aerucin[®] have confirmed the stability and efficacious quality of this antibody. Experimental tests were performed using a refrigerated stable liquid formulation of Aerucin[®]. These in vitro and in vivo studies have demonstrated that: 1) Aerucin[®] binds to more than 90% of *P. aeruginosa* strains tested, 2) Aerucin[®] protected against and treated infection, and 3) the delivery modalities were efficient enough to deliver the required concentration of Aerucin[®] to the target and to demonstrate efficacy in the animal model. Human tissue binding and mouse toxicology evaluations show no human tissue binding and no adverse toxic effects.

A Phase 1 study in healthy volunteers showed that Aerucin[®] has a favorable safety profile and a PK profile consistent with that of IgG immunoglobulins. The highest dose tested was 20 mg/kg, which is the dose selected for this study.

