5 STUDY TREATMENTS

5.1 Treatment Groups

After completing all screening procedures, eligible study subjects will be randomized to one of the following treatment groups:

- Control group: placebo
- Investigational Product group: Aerucin® 20 mg/kg

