5.5.3 Study Drug Administration

The entire content of the bag must then be administered intravenously at room temperature in approximately 2 hours. An in-line 0.2 µm pore filter should be used.

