### 6.3.6. Compliance to Study Drug

Compliance with study drug will be summarized and will be defined as the actual dose of study drug taken divided by intended dose multiplied by 100. Percent compliance as a continuous variable and the proportion of patients with <90% and ≥90% compliance will be summarized by treatment group for the Safety and micro-ITT Populations.

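### The stated 20 mg/kg dose and the written preparation rule do not agree: the protocol's one worked example (120 kg, 20 vials) gives at least 20.6 mg/kg, and the rule at other weights is not stated

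*Protocol*

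**What the plan says.** The dose is given per kilogram throughout. Protocol 5.1 lists the arm as "Investigational Product group: Aerucin® 20 mg/kg", and Protocol 1.2 ties this to phase 1: "The highest dose tested was 20 mg/kg, which is the dose selected for this study".

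The preparation steps are given in vials:

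- Protocol 5.5.1: "The Aerucin[®] drug product is formulated at 27.5 mg/mL", supplied in vials "containing no less than 4.5 mL of extractable volume".
- Protocol 5.5.2: the EDC/IWRS displays a number of vials by weight, and "the content of the selected vials must be transferred into this bag using sterile technique". The bag is labelled with the number of vials used. Subjects above 120 kg get the amount "corresponding to 120 kg, i.e. 20 vials". SAP 3.4 repeats this equivalence.
- Protocol 5.5.3: "The entire content of the bag must then be administered intravenously".

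Protocol 5.5.2 calls its account a summary and leaves the detail to a Pharmacy Manual.

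SAP 6.3.6 has compliance "defined as the actual dose of study drug taken divided by intended dose multiplied by 100", but does not say what the intended dose is. Protocol 5.5.4 judges compliance against the amount shown by the EDC/IWRS.

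**The concern.** As written, no step between vial selection and infusion measures out 20 mg/kg. The subject receives a whole number of vials, and that amount equals 20 mg/kg only at multiples of one vial's content. The protocol's own example is not such a weight.

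Three things are at stake:

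- **Safety margin.** Protocol 1.5.1 and 5.2 rest on phase 1 doses of up to 20 mg/kg. Table 1-1 shows five volunteers at that level. A preparation rule that goes above it should be acknowledged there.
- **Compliance.** The SAP ratio depends on whether the intended dose means 20 mg/kg times weight or the assigned vials.
- **PK.** Protocol 9.3.3 compares patients with healthy volunteers on Cmax, AUC0-28 and mean profiles, and does not mention dose normalisation.

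**Working it through.** **Inputs.** Dose 20 mg/kg (Protocol 5.1); at least 4.5 mL per vial at 27.5 mg/mL (5.5.1); 120 kg equals 20 vials (5.5.2, SAP 3.4).

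**Step 1: the protocol's own figure.**

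- One vial: 4.5 × 27.5 = 123.75 mg, a minimum because 4.5 mL is a minimum.
- 120 kg at 20 mg/kg: 120 × 20 = 2400 mg, and 2400 / 123.75 = 19.39 vials.
- Rounding up gives 20, as stated. Rounding to the nearest vial or down gives 19, which does not match.
- 20 vials: 20 × 123.75 = 2475 mg, and 2475 / 120 = 20.625 mg/kg. Excess: 2475 / 2400 − 1 = 3.1%.

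This step needs no assumption beyond transferring the vials' contents in full, as written.

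**Step 2: other weights, if the count is always rounded up (assumption).** Vials n = ceil(20w / 123.75); dose = 123.75n / w.

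| Weight (kg) | 20w / 123.75 | Vials | mg/kg | Excess |
|---|---|---|---|---|
| 40 | 6.46 | 7 | 21.7 | 8.3% |
| 43.4 | 7.01 | 8 | 22.8 | 14.1% |
| 50 | 8.08 | 9 | 22.3 | 11.4% |
| 70 | 11.31 | 12 | 21.2 | 6.1% |
| 80 | 12.93 | 13 | 20.1 | 0.5% |
| 100 | 16.16 | 17 | 21.0 | 5.2% |
| 120 | 19.39 | 20 | 20.6 | 3.1% |

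Over 40 to 120 kg in 0.1 kg steps, 99.8% of weights exceed 20 mg/kg. The mean is 20.84 mg/kg (+4%) if weights are spread evenly, which is a further assumption.

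The documents set no minimum weight, so the largest excess depends on the lightest subject assumed:

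| Lightest subject (kg) | Largest excess | Reached at (kg) |
|---|---|---|
| 60 | 10.0% | 61.9 |
| 50 | 11.4% | 50.0 |
| 45 | 12.3% | 49.6 |
| 40 | 14.1% | 43.4 |
| 30 | 19.8% | 31.0 |

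**Step 3: other whole-vial rules that also give 20 vials at 120 kg.** One such rule is 120 / 20 = 6 kg per vial. From 40 to 120 kg:

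| Rule | Range (mg/kg) | Weights above 20 mg/kg |
|---|---|---|
| 6 kg per vial, rounded up | 20.6 to 23.5 (+17.6%) | 100% |
| 6 kg per vial, nearest | 19.3 to 22.0 | 90% |
| 6 kg per vial, rounded down | 17.7 to 20.6 | 40% |

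None of these rules delivers 20 mg/kg across the range. Size and direction depend on the rule.

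**Step 4: the compliance ratio, if intended dose meant 20 mg/kg times weight.**

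- A subject given the full capped amount falls below 90% when 2475 / (20w) < 0.9, i.e. w > 137.5 kg.
- A 50 kg subject given 9 vials is assigned 9 × 123.75 = 1113.75 mg against 1000 mg. The 90% threshold is 900 mg, so the subject passes after losing 1 − 900 / 1113.75 = 19% of the bag.

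If intended dose means the assigned amount, both anomalies disappear.

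**The case against.** The strongest reply is that Protocol 5.5.2 is a declared summary, and the Pharmacy Manual, which is not among the documents, may set a partial-vial step or another rounding rule. The section also has saline removed to match the drug volume, so preparation does work with volumes. This stands against any general claim about rounding. A reader might infer that almost every subject is dosed above 20 mg/kg, by up to some fixed percentage. The documents do not support that: rounding up everywhere is inferred from one example, and the maximum depends on an assumed lightest weight. The reply does not remove the mismatch at 120 kg, which is in the protocol text and repeated in the SAP.

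Other replies also have force:

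- **Compliance.** Protocol 5.5.4 already points to the EDC/IWRS amount, so the anomalies in step 4 arise only if the SAP is read against the protocol. What remains is an undefined term.
- **PK.** SAP 6.5 leaves PK to a standalone plan. Dose must already enter the population model, because it pools phase 1 data at 2, 8 and 20 mg/kg. With about eight active patients and five volunteers at 20 mg/kg, a mean shift of about 4% is unlikely to decide the non-compartmental comparison.
- **Cap.** Twenty vials fall below 20 mg/kg above 2475 / 20 = 123.75 kg, but the cap is an openly stated rule, not a contradiction.
- **Traceability.** Vial counts and numbers are already recorded, so nominal mg assigned can be recovered.

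**Conclusion.** The point holds in a limited form. On the documents alone, the stated dose and the preparation rule disagree at the one weight where both can be checked: at least 2475 mg against 2400 mg, or 20.6 against 20 mg/kg (+3.1%). That is above the highest dose tested in phase 1. The text does not support calling it the highest dose ever tested; Protocol 5.2 says only that it was the highest tested at that time.

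Beyond 120 kg as the worked case, the size is conditional. Under universal rounding up, nearly all subjects up to 120 kg exceed 20 mg/kg, by about 4% on average for evenly spread weights, with a maximum of about 10% to 20% for a lightest subject of 60 down to 30 kg. Other rules consistent with the example run from 17.7 mg/kg to 17.6% above 20 mg/kg, from 40 kg up. Any vial content above 4.5 mL would raise the delivered doses.

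Severity is moderate. No effect on the primary Day 21 test, its power or its type I error is shown.

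**What to change.** - Reconcile the synopsis, Protocol 1.2, 5.1, 5.2, 5.5.2 and 5.5.3, SAP 3.4 and the Pharmacy Manual, so that the stated dose, the 120 kg equivalence and the preparation steps agree. State how the vial count is derived at every weight. This point takes no view on which dose or rule is right.
- If whole-vial dosing is kept, state the mg/kg range it delivers and address it against the phase 1 maximum in Protocol 1.5.1 and 5.2.
- Define intended dose in SAP 6.3.6 as the amount assigned by the EDC/IWRS, in line with Protocol 5.5.4, so that subjects dosed by the rule are not misclassified.
- Record actual mg infused. Use it as the dose in the PK analyses and dose-normalise Cmax and AUC0-28 for the healthy-volunteer comparison, unless the separate PK plan already does so.

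The cost is wording in the protocol, SAP, PK plan and Pharmacy Manual, and one or two eCRF fields. The main downside is that the stated dose may have to be given as a range.

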5.5.3 Study Drug Administration

The entire content of the bag must then be administered intravenously at room temperature in approximately 2 hours. An in-line 0.2 µm pore filter should be used.

5.5.4 Treatment Compliance

The study drug will be administered once, intravenously, in a strictly monitored setting. Compliance will be recorded by confirming the start and stop dates and times of the infusion to show that the study drug was administered per the amount indicated by the EDC / IWRS system.

5.5.5 Storage and Accountability

The study drug must be kept refrigerated between 2 and 8° C (35.6 and 46.4° F). Storage temperature is to be monitored and the corresponding records kept on file.

Availability and usage of study drug by the study sites will be recorded using the EDC / IWRS & Inventory system.

5.6 Prior and Concomitant Medications and/or Procedures

5.6.1 Excluded Medications and/or Procedures

Administration of monoclonal antibodies is forbidden for the duration of the study. Patients who received intravenous immunoglobulins (IVIG) within the last 90 days are excluded from the study.

5.6.2 Restricted Medications and/or Procedures

None.

5.6.3 Documentation of Prior and Concomitant Medication Use

All concomitant therapies which are ongoing at the time of Informed Consent signature and/or administered during the course of study through 28 days after study treatment will be recorded in the EDC. This includes both prescription and non-prescription drugs.

In addition to reporting period above, antibiotic therapies administered within 48 hours of study treatment should also be recorded in the EDC, even if they were administered prior to Informed Consent Signature.

6 STUDY PROCEDURES

An overview of the study is provided below (**Figure 6-1**). Day-by-day details are provided in (**Table 6-1**). In summary, any patient with VAP, who is intubated, older than 18 years (at least 20 years of age in Taiwan and at least 19 years of age in South Korea) and who signed an informed consent, will enter a screening phase dedicated to identifying any pathogen that is present, and in particular, verifying whether *P. aeruginosa* is present. This screening phase is critical to ensuring that no potentially eligible patient is missed. Therefore, the related activities should be organized and managed proactively. Participation of key hospital staff is very important, including personnel involved in managing infectious diseases in the institution, the local microbiology department, and any relevant personnel.

If a culture from a valid airway specimen (BAL, mini-BAL or ETA) obtained within 72 hours of randomization is positive for *P. aeruginosa*, the subject can be randomized on this sole basis provided that all eligibility criteria are met, and that a new valid airway specimen is obtained prior to treatment. This baseline airway specimen will be sent to the site's local microbiology laboratory for quantitative/semi-quantitative culture. These baseline culture results are not required prior to randomization.

The sites will obtain airway specimens for culture prior to treatment (baseline), as medically indicated, at time of extubation, and at Day 28 (if not extubated prior to Day 28). Airway specimen cultures will be sent to the local microbiology laboratory for culture, including identification of genus and species, quantification and susceptibility testing as outlined in the microbiology laboratory manual.

Isolates of unique organisms from airway specimen cultures will be sent to the central lab. The central microbiology laboratory will confirm identification and perform standardized antibiotic quantitative/semi-quantitative culture, susceptibility testing and serotyping on target pathogens as outlined in the microbiology laboratory manual.

If the results of an airway specimen obtained within 72 hours of randomization are not available, a valid airway specimen (BAL, mini-BAL or ETA) should be obtained and tested using rapid diagnostic testing (see section **14.3**) if available at site and approved to use by the Regulatory Authorities (RA) / Independent Ethics Committee (IEC). If such rapid testing is positive for *P. aeruginosa*, the subject can be randomized on this sole basis.

The same airway specimen used for rapid testing will be assessed at the site's local laboratory for baseline culture including identification of genus and species, quantitative/semi-quantitative culture and susceptibility testing as outlined in the laboratory procedure manual. These baseline culture results are not required prior to randomization.

Isolates of unique organisms will be sent to the central lab. The central microbiology laboratory will confirm identification, perform the standardized antibiotic susceptibility testing, and serotyping.

If no rapid diagnostic test is available and no culture within 72 hours of randomization has been taken, the site should make all possible efforts to have an airway specimen (BAL, mini-BAL or ETA) collected and sent to their local microbiology lab as soon as possible. The randomization cannot be done in this case until the microbiology results of a positive *P. aeruginosa* culture have been confirmed.

As soon as *P. aeruginosa* is confirmed on a valid airway specimen and all other inclusion and exclusion criteria are met, the subject should be randomized and treated (more than one pathogen allowed, if *P. aeruginosa* is regarded a key pneumonia causing pathogen). The study personnel will randomize the subject using the EDC / IWRS system to either Aerucin® 20 mg/kg or placebo.

Upon randomization, PK evaluations will be initiated as detailed in section 7.4.

Following treatment, all patients will be assessed daily for overall clinical status, as detailed below (see Section 6.5), based on information collected as medically required. In addition, complete assessments will be performed on Day 4, 7, 14, 21 and 28, as detailed below (see Section 6.6).

Methods are described in detail in the Laboratory Manual.

Figure 6-1 Protocol Overview
Study Design: Protocol AR-105-002

[figure not shown]

Table 6-1 Schedule of Assessments

Visit	Screening, Baseline, and Randomization	Treatment	Follow-up (Daily until index pneumonia is considered resolved)	Follow-up Any setting	End of Study ¹⁴ or Early Termination ¹⁷
Day	-1	0	1 to 28 Daily	4, 7, 14, 21	28 or Day of Termination
Informed Consent	X				
Eligibility	X				
Demographics	X				
Type of Pneumonia ¹⁰	X				
Medical history	X				
Surgical History	X				
Case history	X				
Concomitant medications	X	X	X	X	X
Physical exam	X			X	X
Vital signs ¹¹	X	X	X	X	X
12-lead ECG	X				
Safety laboratory tests	X		X ¹	X	X
Sampling: ADA	X ³				X
Sampling: Future Biomarkers (where applicable)				X	X
Sampling: PK	X ⁴	X ^{5,6}	X ^{5,6}	X ^{5,6}	X ^{5,6}
Microbiology: rapid testing	X				
Microbiology: classic	X		X ¹	X ¹	X ¹
Sampling: microbiology	X		X ¹	X ¹	X ¹
Respiratory data	X	X ²	X ¹	X	X
Arterial gases or pulse oximetry ¹⁶	X	X		X	X
PaO ₂ /FiO ₂ ratio	X	X	X	X	X
APACHE II	X				
SOFA	X	X	X ²		
Randomization	X ⁷				
Treatment		X			
Assessment of Clinical Cure			X ⁸	X	X
Adverse events		X	X	X	X
Chest X-Rays	X ¹²				
Pregnancy Test (Urine or Serum)	X ¹³				
Discharge data					X ⁹
Study Follow-Up Phone Call				X ¹⁵	X ¹⁵

Visit	Screening, Baseline, and Randomization	Treatment	Follow-up (Daily until index pneumonia is considered resolved)	Follow-up Any setting	End of Study ¹⁴ or Early Termination ¹⁷
Day	-1	0	1 to 28 Daily	4, 7, 14, 21	28 or Day of Termination

 1. To be performed if medically necessary. Follow-up airway specimens to be obtained as medically necessary and prior to extubation and at Day 28 (if not extubated prior to then) for quantitative or semi-quantitative culture. 2. SOFA and respiratory data to be collected on Day 0, 12 hours after treatment initiation and on Day 4, 7, 14, 21, 28 while intubated and mechanically ventilated. Parameters for SOFA score calculation should not be older than 72 hours. 3. ADA only at screening / baseline and Day 28, or at early termination. 4. Pre-dose PK sample to be obtained prior to treatment initiation. 5. PK samples to be obtained for the FULL PK sub-study at the following times after initiation of treatment: 2 hours (end of infusion), 4h, 12h, and 24 hours and 1 sample at each of the following visits: Day 4, 7, 14, 21, and 28. 6. PK samples for the SPARSE PK sub-study at the following times after initiation of treatment: 1 sample at 2 hours (end of infusion), 1 sample at either 4h, 12h, or 24 hours post-treatment initiation (inclusive) and 1 sample at any of the following visits: Day 4, 7, 14, 21, or 28. 7. Eligible subjects are randomized on Day -1, Treatment day is Day 0 for the purpose of monitoring and collecting the required samples over the first 24 hours. 8. Clinical Cure will be assessed at Day 7, 14, 21, 28 for the analytical purposes. 9. Discharge data to be obtained when discharge occurs or Day 28, whichever occurs first. 10. Patients with pneumonia who are intubated are eligible for screening regardless of the type of pneumonia, which will be recorded at the time of screening for all study subjects. 11. Vital signs will be recorded at baseline prior to treatment (time 0) and then at 1, 2, 4, 12, and 24 hours post treatment. Vital signs will also be recorded daily thereafter. 12. In addition to the screening timepoint, chest x-ray(s) are to be taken at any time as medically indicated. 13. Women of child bearing potential must take a urine or serum pregnancy test at the time of Screening. 14. For subjects with early discharge, effort must be made to perform all protocol defined procedures outlined for End of Study/Early Termination. 15. Subjects who decide to discontinue study assessments prior to Day 28 will receive a study exit safety follow-up phone call on key days (Day 4, 7, 14, 21, 28) until Day 28 (+7 days) to assess Clinical Cure, survival and the status of any adverse events. 16. Changes in PaO₂/FiO₂ ratio (e.g. by arterial blood gases), if available and whenever possible OR changes in non-invasive measures of oxygenation (e.g. by pulse oximetry) 17. A few days before or after the specified date is acceptable (± 2 days) 					
